Following enrollment, baseline data and selected outcome markers will be assessed. Then all patients will undergo a 4-week care optimization phase during which time we will review the patient's dialysis care and make adjustments (if necessary) to meet standard of care guidelines as defined by CMS, KDOQI and KDIGO (Table 1). Outcome markers will be reassessed again after completion of the 4-week care optimization phase. At this time all patients will also undergo a baseline exercise test to measure peak VO₂ and a DXA scan for body composition analysis before starting EMS training.

| Table 1 | |
|---------------------------|--|
| Parameter | Optimized care goals |
| Vascular access | Discontinuation of central venous catheter and use of arteriovenous access |
| Fluid removal | Optimize dry weight. Limit UF rate to ≤ 13 ml/kg/hr |
| Solute removal | Minimum dialysis time ≥ 3.5 hours. Goal 4 hours. kT/V ≥ 1.4 |
| Acid-base | Pre-dialysis HCO ₃ between 22-27 mEq/L |
| Anemia | Hemoglobin 9.5-11 g/L, if on erythropoietin; Iron saturation $\geq 20\%$ |
| Ca, PO ₄ , PTH | Calcium, PO ₄ within normal levels; PTH ≤ 600 pg/ml |

EMS training will be done while the patient is on hemodialysis. At the first EMS training session, optimal EMS settings will be established and patients will be taught how to apply the electrodes and use the muscle stimulator. For patients who agree we will also do a muscle biopsy of the quadriceps (vastus lateralis) muscle at this first training visit before starting EMS training. Patients will be seen at the next dialysis session and again after 7 days to confirm that they are doing the EMS training properly. Patients are then seen at Day 14, 28, 42, 56, 84 and 112 after starting EMS training to assess for any adverse events, monitor progress with EMS training and adjust the EMS settings to make sure they are at the optimal tolerated intensity of muscle stimulation. The EMS training will continue for 16 weeks. At Day 56 and Day 112 (8 and 16 weeks) of EMS-training all the primary and secondary outcome variables including exercise stress test for peak VO₂ and DXA scan will be performed. For patients who agree we will also perform a muscle biopsy at a dialysis visit around Day 56 and Day 112 (not the same day as the exercise stress test). One month after stopping EMS training the patient will be seen and the outcome variables will be repeated except for the DXA scan and the exercise stress test.

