2. Intervention. EMS is delivered to the quadriceps muscle groups using a neuromuscular electrical stimulator (using either the EMPI 300PV or its replacement, the Continuum device, EMPI, Inc). The device generates electrical impulses that are delivered to nerves stimulating the muscles through electrodes applied to the skin surface. Patients are taught how to place the adherent electrode pads over the quadriceps muscles on the upper thigh a few inches below the anterior iliac crest and just above the patella bilaterally. The electrodes will be applied at home or after coming to the dialysis unit just prior to each dialysis session. The patient's legs are extended straight on the reclining dialysis chair. The device is set to deliver biphasic electrical stimulation at 1-20 Hz and a pulse duration of 400 μ s applied for 1-12 seconds on and 1-12 seconds off. The stimulus intensity (typically 10-100 mA) is gradually increased to the maximum tolerable level for muscle contraction. The patient will feel contraction of the muscles and may feel mild shortness of breath and tingling of the skin but otherwise is expected to tolerate the stimulation well. The stimulation is delivered to one side for 15 minutes and then to the

opposite side for 15 minutes. This will be repeated at each dialysis session 3x/week. The first intervention will be observed through the entire treatment. If the patient feels excessively fatigued or other untoward signs the stimulator will be turned off until they feel better and then restarted to achieve the full treatment time.

At each study visit the study coordinator will confirm that the settings are correct and readjust the maximal tolerated stimulus intensity as needed to account for training. Patients will also be encouraged to be active and exercise as much as possible outside of the dialysis unit.

The total duration of the study for any patient is expected to be 6 months. We plan to complete the study of all patients within 2 years.

3. Study population.

Patients on hemodialysis three times a week at participating study sites within the UIHC dialysis program will be eligible to participate.

3.1 Inclusion & exclusion criteria.

Inclusion criteria include: age over 18 year old, able to provide informed consent, on maintenance hemodialysis for end stage renal disease and expected to stay in a participating dialysis unit for at least 6 months.

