- Fasting blood sample (30 ml) for:
 - o Insulin and glucose
 - o Interleukin-6 (IL-6), tumor necrosis factor alpha (TNF α), C-reactive protein
 - o Glutathione (reduced and oxidized forms), glutathione peroxidase (GPx), superoxide dismutase (SOD), catalase (CAT), F2 isoprostane and protein thiols.
- Measure quadriceps muscle strength (bilaterally)
- 48 hour activity monitoring (using wrist watch monitor between dialysis sessions).
- DXA scan (performed in CRU)

- Perform exercise stress test to determine peak VO₂ (performed in CRU)

5.3 Visit 3. Initiate EMS training (Day 0). Performed in dialysis unit and CRU. 60-75 minutes. 30 minutes extra for optional muscle biopsy, if performed.

- Perform pre-EMS muscle biopsy before starting dialysis (optional)
- EMS training is done while on hemodialysis starting approximately 30 min after dialysis initiation.
 - o Record pre-EMS blood pressure and pulse
 - o Initiate EMS training on quadriceps muscle of leg not used for muscle biopsy for 15 minutes while on dialysis
 - o Measure and record BP and pulse before and just prior to completion of EMS training.
 - o Record any symptoms related to EMS
 - o Train patient how to use EMS device.

5.4 . Visits 4-8, 11. EMS training visits (Day 2/3 and 7). Performed in dialysis unit. Time required up to 45 minutes.

- Record any new medical conditions, symptoms or complaints
- Observe patient initiate and perform EMS training.
 - o Adjust stimulus intensity to maximum tolerated by patient for both legs
- Record EMS setting used.
- Record pre-dialysis sitting BP and pulse
- Record post-dialysis sitting BP and pulse

5.5 Visits 9 &12. Outcome assessment visits (Day 56 & 112 ± 7 days). Performed in dialysis unit or CRU where specified. Time required up to 4 hours.

- Record any new medical conditions, symptoms or complaints
- Record current dialysis orders
- Record episodes of dialysis hypotension (SBP<90 or symptoms needing saline, last 6 HD sessions)
- Record current exercise status (minutes of exercise per week)
- Record concomitant medications
- Malnutrition-inflammation (MIS) assessment
- Kidney Disease Quality of Life-36 (KDQOL-36) assessment
- Patient Health Questionnaire-9 (PHQ-9)
- Record vital sign measurements (predialysis or non-dialysis day, same timing as baseline measures)
- 6-minute walk test
- Record weight, waist circumference, hip circumference
- Record thigh circumference bilaterally
- Record most recent dialysis monthly lab tests.

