A prior study of EMS during hemodialysis found that EMS produced a statistically significant increase in BP (SBP increased by 8 mmHg and DBP increased by 3 mmHg) while the device was turned on compared to when it was turned off.²⁹ Overall the average BP on dialysis was higher when people used EMS for 15 minutes out of every hour while on dialysis compared to no EMS (average BP = 125/66 with intermittent EMS compared to 121/64 when no EMS was performed). Fewer hypotensive episodes during a dialysis session were seen when patients used intermittent EMS compared to no EMS.

6.2.5. Fracture. Stress testing or EMS could lead to a bone fracture particularly in a patient with severe osteoporosis but this is considered unlikely to occur. EMS is also being studied as a mechanism to prevent osteoporosis.

6.2.5. Dizziness or confusion. Dizziness or confusion occurring during the exercise stress test or during an EMS training session is grounds for terminating the exercise and monitoring the patient until the symptoms resolve. The study physician will evaluate the circumstances of the event to decide whether further evaluation is needed and whether the patient can continue in the study.

6.2.6. Hypoglycemia. Low blood sugar with exercise might occur particularly in patients who are diabetic. If symptoms of hypoglycemia occur then the exercise will be terminated and sugar administered to the patient. A blood sugar will be measured and the study physician notified. This is unlikely to occur during EMS as the patient will be on hemodialysis, which provides glucose in the dialysate.

6.3. Risk of phlebotomy.

Phlebotomy may cause discomfort due to needle puncture, hematoma formation, blood loss, infection or syncope. It will be performed at the time of dialysis from your dialysis needle by trained personnel to limit risk.

6.4. Risk of radiation from a DXA scan.

A DXA scan delivers a dose of radiation that is approximately one tenth that of a standard chest X-ray and equivalent to the dose of radiation received during one-day exposure to natural background radiation.

6.5. Risk of taking health and depression assessment questionnaires.

Questions about personal health or depression might raise anxiety or concerns about personal health. If this occurs these will be addressed with the patient by a member of the study team or referred to their primary provider or social worker as appropriate.

6.6. Risk of a muscle biopsy under ultrasound guidance.

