In Affymetrix Human Exon 1.0 ST arrays, the log2 hybridization signal reflects the mean signal intensity of all exon probes specific for an individual mRNA, and is proportional to the level of that mRNA. We will perform two main comparisons: 1) the effect of acute exercise comparing the gene expression levels 4 hours after the first EMS training to baseline before training and 2) the effect of chronic EMS training (8 and 16 weeks) compared to the Pre-EMS training sample. We will restrict the analysis to mRNA's that have a mean log2 hybridization signal of >5 in either the pre-EMS sample or the 8 or 16 week EMS treatment conditions. We will use paired t-tests to determine which of the remaining mRNA's are present at a significantly different level (adjusting for the false discovery rate inherent in multiple testing) in the EMS treatment compared to the baseline sample. The list of differentially expressed genes will be examined for important biological pathways relating to muscle glucose metabolism and insulin response, mitochondrial biogenesis and function, muscle phenotype, growth and energy metabolism, oxidant stress and inflammation. We will also use bioinformatics tools such as Onto-Express to help translate the list of differentially expressed genes into functional categories such as biological process or cellular role based on the annotation using Gene Ontology terms. All microarray data will be deposited in the GEO database.

10. References

1. U.S. Renal Data System, *USRDS 2012 Annual Data report: Atlas of End-Stage Renal Disease in the United States*, National Institutes of Health, National Institute of Diabetes and Digestive and Kidney Diseases, Bethesda, MD, . 2012.
2. Carrero JJ, de Jager DJ, Verduijn M, et al. Cardiovascular and noncardiovascular mortality among men and women starting dialysis. *Clin J Am Soc Nephrol*. Jul 2011;6(7):1722-1730.
5. Johansen KL. Exercise in the end-stage renal disease population. *J Am Soc Nephrol*. Jun 2007;18(6):1845-1854.

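### Comparison 1 of the gene expression analysis cannot separate the first EMS session from the dialysis session around it, so it should be described as their combined effect

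*Combined protocol and SAP*

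**What the plan says.** Section 9.8 names two main comparisons. The first is "the effect of acute exercise comparing the gene expression levels 4 hours after the first EMS training to baseline before training"; the second sets weeks 8 and 16 against the pre-EMS sample. For the analysis: "We will use paired t-tests to determine which of the remaining mRNA's are present at a significantly different level", with adjustment for false discovery. Section 4.2.12 gives the purpose as learning which pathways EMS activates, both acutely and with training.

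The timing comes from other sections:

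- Section 5.3, Visit 3, baseline sample: "Perform pre-EMS muscle biopsy before starting dialysis (optional").
- Section 5.3, stimulation: "EMS training is done while on hemodialysis starting approximately 30 min after dialysis initiation".
- Section 5.3, leg: "Initiate EMS training on quadriceps muscle of leg not used for muscle biopsy for 15 minutes while on dialysis".
- Section C.2 describes EMS sessions differently: "The stimulation is delivered to one side for 15 minutes and then to the" opposite side for the same time.
- Table 1 in Section C.1, session length: "Minimum dialysis time ≥ 3.5 hours. Goal 4 hours".

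The sections disagree on whether the 4-hour sample exists. Section 8 allows up to four biopsies, one of them after the first EMS treatment, and Section 9.8 analyses it. Section 9.7 lists three time points without it, Section 4.2.12 lists the same three while also describing an acute analysis, and the Visit 3 procedures contain only the pre-dialysis biopsy.

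**The concern.** A before-after difference can be called an EMS effect only if EMS is the one relevant thing that happened between the samples. Here dialysis also lies between them. The pathways named in advance include glucose metabolism and insulin response, oxidant stress and inflammation. It is plausible that a dialysis session itself touches some of these; Section 6.2.6 notes that "the patient will be on hemodialysis, which provides glucose in the dialysate". A gene that responds to dialysis would be listed as a gene that responds to EMS, and a gene on which the two act in opposite directions could be missed.

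The label could also travel. Section 4.2.12 expresses interest in setting these profiles beside volitional exercise and beside patients with other levels of kidney function, and Section 9.8 deposits the data publicly. Patients who are not on dialysis would have no session between their samples, so a dialysis response could pass for a difference due to kidney function.

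The plan does use an EMS-free comparator elsewhere. Section 4.2.11 compares blood pressure and hypotensive episodes in EMS sessions with sessions without EMS. The gene contrast has no counterpart.

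**Working it through.** The plan states no sample size, power or effect size for the gene contrast, so there is no figure to reproduce. The check is a timeline and a question of what the contrast estimates.

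**Timeline.** Inputs: EMS starts 30 min after dialysis starts (5.3); EMS lasts 15 min for one leg (5.3) or 15 + 15 = 30 min for both (C.2); the sample is 4 h = 240 min after EMS (9.8); dialysis lasts 210 min at minimum, with a goal of 240 min (Table 1). The plan does not say whether the 4 hours run from the start or the end of EMS, so all readings are shown.

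Sample time after dialysis start = 30 + EMS duration counted + 240. Time after dialysis ends = that figure minus session length.

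| 4 hours counted from | After dialysis start | After a 210-min session ends | After a 240-min session ends |
|---|---|---|---|
| EMS start | 30 + 0 + 240 = 270 min | 60 min | 30 min |
| End of one leg | 30 + 15 + 240 = 285 min | 75 min | 45 min |
| End of both legs | 30 + 30 + 240 = 300 min | 90 min | 60 min |

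The sample falls 4.5 to 5.0 h after dialysis starts and 30 to 90 min after it ends. It would fall inside the session only if dialysis ran beyond 270 to 300 min, and the pair would still differ by hours of dialysis.

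**What the contrast estimates.** For each gene, the mean paired difference is the EMS effect plus the dialysis effect plus anything else that changes over those hours. Separating the first two needs a sample after dialysis without EMS, or a comparison group. The plan has one group, and every later biopsy follows EMS training. Pairing removes stable differences between patients, and false discovery adjustment limits chance findings. Neither removes a real shift credited to the wrong cause.

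**The leg.** If Section 5.3 is followed, the 4-hour sample is either from the biopsied leg, which is unstimulated and was biopsied earlier the same day, or from the stimulated leg, which is not the baseline leg. If Section C.2 is followed, both legs are stimulated and a same-leg pair is possible. The dialysis overlap is the same either way.

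**Possible size, under assumptions.** Take a gene with no EMS effect and a dialysis shift of 1 SD of the paired difference. A two-sided paired t-test at unadjusted P<0.05 flags it with probability 0.40, 0.80 and 0.95 for 5, 10 and 15 pairs. For a shift of 0.5 SD the figures are 0.14, 0.29 and 0.44.

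Now simulate a list: 10,000 mRNAs, 500 moved by dialysis only, EMS doing nothing, within-patient SD 0.3 log2 (SD of the difference 0.3 × √2) and a 5% false discovery rate. A 1 log2 shift lists about 200 genes with 6 pairs, 480 with 8 and 525 with 15. A 0.5 log2 shift lists about 0 with 6 pairs and 400 with 15. With SD 0.6, a 1 log2 shift lists about 0 with 6 pairs. The range is about 0 to 525, and every input is assumed.

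**The case against.** The strongest reply is that the procedural text does not collect this sample. Visit 3 has one biopsy, Section 9.7 has three time points, and the expression filter in Section 9.8 itself names only the pre-EMS, 8-week and 16-week samples. If the acute sample were struck, the point would vanish. This stands as a condition: the concern applies if the sample is taken. It does not dispose of the matter, because Section 8 counts the sample and Section 9.8 makes it one of two main comparisons.

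Next, nothing in the documents shows that dialysis shifts quadriceps mRNA. That also stands. The simulated counts show only that false attribution could range from nothing to several hundred genes. A reader might be tempted by the clock instead: EMS fills 15/285 = 5% to 30/270 = 11% of the time from dialysis start to the sample. Share of time is not share of effect, so this does not measure bias. Nor is it the true interval between the samples, since the gap between the baseline biopsy and dialysis start is not given.

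Finally, the leg argument depends on which section governs. A reader might infer that the 4-hour sample must be unstimulated or mismatched muscle. The documents do not settle that, because the sampled leg is unstated and Sections 5.3 and C.2 differ.

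The optional, exploratory nature of the biopsies in a pilot of up to 15 patients limits the consequence, but not the error in the label.

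**Conclusion.** The point holds conditionally. If the 4-hour sample is collected, comparison 1 estimates the joint effect of one dialysis session and the first EMS session, and the plan cannot divide it. This rests on the plan's own times and on sessions no longer than about 4.5 to 5.0 h; longer sessions would weaken the overlap without removing it.

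Three stronger readings are not supported. One is that dialysis genes will in fact be reported as EMS genes: collection of the sample is unsettled, and the size of a dialysis response is unknown. Another is that the chronic contrast offers a clean basis for EMS claims: it too is an uncontrolled before-after change, with biopsy timing relative to dialysis unstated at weeks 8 and 16. The third is that the trial's main result is affected: the analysis of HOMA-IR and LAR does not use these samples. The consequence is a wrong label on one part of an optional secondary outcome, worth correcting because the correction is cheap and changes what may be concluded.

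**What to change.** - In Sections 9.8 and 4.2.12, redefine comparison 1 as the combined acute effect of one hemodialysis session with EMS. State that its genes and pathways will not be attributed to EMS alone, including in any later comparison with volitional exercise or across levels of kidney function.
- Reconcile Sections 8 and 9.8, which include a sample after the first EMS, with the biopsy lists in Sections 4.2.12, 5.3 and 9.7, which do not. If the sample is kept, say whether the 4 hours run from the start or the end of EMS.
- Reconcile Section 5.3 with Section C.2 on which legs are stimulated at the first session, and state which leg each biopsy comes from.
- Describe the week 8 and 16 contrast as an uncontrolled before-after change as well.

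These are changes of wording and consistency; they add no biopsy and no patient. The cost is a narrower claim: comparison 1 no longer speaks to EMS by itself.

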treatment and after 8 and 16 weeks of EMS training to determine the chronic effect of EMS training on muscle gene expression. Gene expression analysis will be done using Affymetrix Human Exon 1.0 ST arrays as previously described.⁷⁰ We will first examine specific genes that are highly overexpressed or under-expressed after acute and chronic exercise compared to the baseline (pre-EMS). We will also look for biological pathways activated or suppressed by acute and chronic exercise specifically looking at pathways relating to muscle glucose metabolism and insulin response, mitochondrial biogenesis and function, muscle phenotype, growth and energy metabolism, oxidant stress and inflammation. A future goal of this research is to compare the gene expression response to EMS in this study with that seen in patients with normal renal function and varying levels of CKD to see if the gene response profile is qualitatively different in patients with varying levels of kidney function. We are also interested how the gene expression profiles seen with EMS compare to that seen with traditional volitional aerobic exercise to determine if EMS activates different genes or biological pathways than volitional exercise.

5. Visits & Assessments.

Patients will be identified from the population of patients on regular maintenance hemodialysis at one of the University of Iowa dialysis units. Potential subjects will be approached at a dialysis visit and informed of the study.

5.1. Visit 1. If they indicate an interest in participating we will proceed with obtaining written informed consent and confirm that they meet all the inclusion criteria and none of the exclusion criteria.

- Obtain informed consent to participate and consent to access additional appropriate medical records
- Review inclusion and exclusion criteria

Baseline data collection (Day -35 to -28). Performed at dialysis unit or CRU as appropriate. Up to 4 hours time.

- Record demographics and baseline disease characteristics
- Record past medical history and current review of symptoms
- Record current dialysis orders
- Record episodes of dialysis hypotension (SBP<90 or symptoms needing saline, last 6 HD sessions)
- Record baseline exercise status (minutes of exercise per week)
- Record concomitant medications
- Malnutrition-inflammation (MIS) assessment
- Kidney Disease Quality of Life-36 (KDQOL-36) assessment
- Patient Health Questionnaire-9 (PHQ-9)
- Record sitting blood pressure and pulse

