8. Statistical analysis/Power calculations.

This is a pilot feasibility and preliminary efficacy study to determine whether EMS can be delivered to this population and to assess the magnitude of the change and variability in the primary and secondary outcome measures. Data derived from this study will allow planning of a larger randomized controlled study. We plan to recruit up to 15 patients into the trial and complete the trial within 1 year. There will be 5 measurements of the primary and most of the secondary outcome variables in each patient. These will be performed at enrollment, after 4 weeks of "dialysis care

optimization" before starting the EMS intervention, then at 8 and 16 weeks after initiation of the EMS intervention and finally 4 weeks after stopping EMS. The DXA scan, measurement of peak VO₂ will only be performed three times (before starting EMS and then again at 8 and 16 weeks of EMS training). The optional muscle biopsy for gene expression analysis will be performed up to 4 times in patients who agree to this analysis (before and after the first EMS treatment, at 8 and 16 weeks of EMS training). Summary statistics will be used to describe and analyze the data. Changes over time in the outcome variables will be analyzed using the Friedman analysis of variance by ranks to determine if there was a statistically significant effect of EMS. A P<0.05 will be considered statistically significant. Regression analysis will be used to determine if the change in HOMA-IR or LAR is correlated with the magnitude of the observed exercise training effect (i.e. the increase in peak VO₂ or quadriceps muscle strength at 4 months) or maximum intensity of EMS stimulation used during training.

Based on an estimated baseline mean (\pm SD) HOMA-IR score of 4.8 (\pm 1.7) mg/dl· μ U/ml, a sample size of 15 patients will provide 80% power to detect a 28% decrease in the HOMA-IR score (by a paired t-test analysis) at the P=0.05 level. This decrease in HOMA-IR score would be predicted to be associated with a clinically significant reduction in mortality.³³

9. Selected methods

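### The expression filter in Section 9.8 ignores the 4-hour sample, so a gene detectable only after the first EMS session would be removed before the acute comparison is tested

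*Combined protocol and SAP*

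**What the plan says.** Section 9.8 sets out the array analysis in three consecutive steps.

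1. It names two main comparisons. The first is "the effect of acute exercise comparing the gene expression levels 4 hours after the first EMS training to baseline before training". The second is "the effect of chronic EMS training (8 and 16 weeks) compared to the Pre-EMS training sample".
2. It then restricts the analysis, without saying which of the two, to mRNAs with a "mean log2 hybridization signal of >5 in either the pre-EMS sample or the 8 or 16 week EMS treatment conditions".
3. It tests only what survives: "We will use paired t-tests to determine which of the remaining mRNA's are present at a significantly different level", with the qualification "adjusting for the false discovery rate inherent in multiple testing". No false-discovery level is given.

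No other expression filter appears anywhere for the acute comparison. Section 4.2.12 makes the acute response a stated interest. It wants insight into pathways activated acutely as well as by chronic training, and it plans to look first at genes strongly raised or lowered after each.

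**The concern.** A detection filter should let through any gene that is detectable in at least one of the samples being compared. The rule does this for the chronic comparison, because all three of that comparison's samples are in it. For the acute comparison it looks at only one of the two samples, the pre-EMS one. Because filtering comes before testing, a gene that fails the filter gets no acute test, and it cannot reach the pathway and Gene Ontology work built on the list of differentially expressed genes. A gene that is silent at rest, switched on for some hours by the first session, and silent again at the later biopsies is one of the responses an acute comparison could be expected to show. Under the present sentence it could not appear.

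**Working it through.** There is no figure in the plan to reproduce. The check is on the logic of the rule.

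**Inputs (all from Section 9.8).** Cut-off: mean log2 signal above 5. Samples in the filter: pre-EMS, week 8, week 16. Samples in the acute comparison: pre-EMS, 4 hours. Samples in the chronic comparison: pre-EMS, week 8, week 16. Order: filter, then paired t-tests.

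**Step 1: enumerate the patterns.** Each of four samples is either above 5 or not, giving 2 × 2 × 2 × 2 = 16 patterns.

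| Rule | Keeps a gene if above 5 at | Patterns kept |
|---|---|---|
| As written | pre-EMS, week 8 or week 16 | 16 − 2 = 14 |
| As written, plus the 4-hour sample | pre-EMS, 4 h, week 8 or week 16 | 16 − 1 = 15 |

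The two rules differ in one pattern only: 5 or less at pre-EMS, week 8 and week 16, and above 5 at 4 hours. The other 15 are treated alike. These are counts of patterns, not of genes, and carry no information about how common each pattern is.

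**Step 2: direction of the loss.** In the lost pattern the pre-EMS mean is at most 5 and the 4-hour mean exceeds 5, so the change is always a rise. A gene above 5 pre-EMS that falls at 4 hours passes the filter on its pre-EMS mean. The loss is therefore confined to induced genes.

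**Step 3: does a large effect protect a gene?** No. Fold change = 2^(4-hour mean − pre-EMS mean). The signal levels below are assumed for illustration and are not in the documents; week-8 and week-16 means are taken as 5 or less.

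| Pre-EMS mean | 4-hour mean | Difference | Fold rise | Outcome under the rule |
|---|---|---|---|---|
| 4.5 | 6.0 | 1.5 | 2.8 | removed untested |
| 4.0 | 7.0 | 3.0 | 8 | removed untested |
| 4.0 | 8.0 | 4.0 | 16 | removed untested |

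**Step 4: check the per-comparison rule.** For the acute comparison, requiring above 5 at pre-EMS or 4 hours keeps 16 − 4 = 12 patterns. Relative to the rule as written it gains the one lost pattern. It drops three in which neither acute sample is above 5 but week 8, week 16 or both are: 14 + 1 − 3 = 12. For the chronic comparison the 14 patterns are unchanged.

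**Step 5: is there a 4-hour sample?** The documents disagree.

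- Implying an acute biopsy: Section 8, which allows up to four biopsies ("before and after the first EMS treatment, at 8 and 16 weeks of EMS training"), and the first comparison in Section 9.8. Section 4.2.12 also speaks of acute effects.
- Not scheduling one: the Overview in Part C (first training visit before EMS, then around Days 56 and 112); the biopsy list in Section 4.2.12; Visit 3 in Section 5.3 (pre-EMS biopsy only); Visits 10 and 13 in Section 5.6; and Section 9.7 (three time points).

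**The case against.** The strongest reply is that this is a by-product of the biopsy conflict. The filter names exactly the three samples that the visit schedule and Section 9.7 provide. On that reading the filter fits the design and it is the acute text that is out of step. This stands in part: without an acute sample the gap has no consequence. But Section 9.8 still lists the acute comparison as one of two main ones, and adding the biopsy to the schedule would not by itself repair the filter.

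A second reply is that the filter was meant for the chronic comparison alone, since it follows that comparison and lists only its samples. The wording covers the analysis as a whole straight after both comparisons are named, which favours the broader reading without settling it. If the narrower meaning was intended, the acute comparison has no stated filter and the sentence still needs changing.

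Third, the stakes are low. The biopsy is optional, the study is a pilot of up to 15 patients, and the array data are to be deposited publicly, so the filter could be re-run. All of that stands, and it limits the weight of the point.

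Two stronger readings are tempting and are not supported. A reader might infer that comparing the acute with the chronic gene list would be biased towards overlap. No such contrast is planned: each condition is compared with pre-EMS, and the future contrasts in Section 4.2.12 concern level of kidney function and volitional exercise. A reader might also infer that all acutely induced genes with low resting expression are lost. They are not: a gene is lost only if its means at both week 8 and week 16 are also 5 or less.

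**Conclusion.** The point holds in a conditional form. As Section 9.8 is written, mRNAs above 5 only at 4 hours are excluded from the acute comparison before testing, regardless of the size of the rise, and the exclusion affects induced genes only. That works against an aim stated in Section 4.2.12. It rests on two assumptions: that the filter applies to both comparisons, and that a 4-hour sample is actually taken. How many of the more than 17,000 transcripts on the array are affected cannot be computed from the documents and could be few. The chronic comparison, the primary outcome and the sample size are unaffected. This is a minor improvement to an optional exploratory analysis.

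**What to change.** State the cut-off for each comparison in Section 9.8: for the acute comparison, mean log2 signal above 5 in the pre-EMS or the 4-hour sample; for the chronic comparison, above 5 in the pre-EMS, week-8 or week-16 sample. Apply the false-discovery adjustment within each filtered set. Settle this before the array data are seen.

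Reconcile the biopsy time points across the Part C Overview and Sections 4.2.12, 5.3, 5.6, 8, 9.7 and 9.8, so that it is clear whether an acute sample exists. If the acute comparison is dropped, leave the filter as it is and delete the first comparison from Section 9.8.

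The filter change costs one sentence and needs no samples or arrays beyond those Sections 8 and 9.8 already describe. It has no effect until the biopsy schedule is reconciled, which is a separate edit.
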